## INTRODUCTION

Myopia known as “short sightedness” causes blurring of vision for distant objects but clearer for near objects. In myopic eyes, the light comes to a focus point before it reaches the retina. When moving closer to an object, this changes the focusing of the light and the object is then in focus on the retina and so looks clearer. Myopia depends on the length of the globe, the corneal steepness, and the lens power.

Classification of myopia:

- Mild myopia: power up to - 4.00 diopters (D)
- Moderate myopia: -4.00D to -8.00D
- High myopia: > -8.00D

ICL implantation can correct myopia, hyperopia, or astigmatism, with clinical and visual results as good as or better than laser procedures. Patients who are not suitable candidates for corneal reshaping procedures, and in whom optical correction with spectacles or contact lenses is either challenging or have poor results, can benefit from ICL surgery.

One of the problems for LASIK application for myopic patients is the risk of post-LASIK ectasia which is believed to be reduced using femto LASIK and the ability of creation of smaller flap thickness. Less high order aberrations are induced with femto LASIK compared to the conventional approach. Results in terms of contrast sensitivity, especially in high spatial frequencies, are better with femto LASIK compared to the conventional method.

This study evaluates the effect of each modality treatment on the visual outcomes in treatment moderate myopic patients.

Phakic intraocular lenses (PIOLs) are generally accepted as an alternative treatment for ametropic correction among different types of refractive correction. Rapid visual recovery, high efficacy, predictability and stability of visual quality, preservation of accommodation, and reversibility are several privileges that have been attributed to PIOL implantation.

The Visian Implantable Collamer Lens (ICL; STAAR Surgical Co, Monrovia, California) is approved by the United States Food and Drug Administration (FDA) for the treatment of moderate to severe myopia. The lens material, trade-named Collamer, is a hydrophilic collagen-polymer combination with a water content of 34% and a refractive index of 1.45.

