Recently, a new ICL (V4c) , with a 360  $\mu\text{m}$  central hole that allows for the natural flow of aqueous humor without the need for a peripheral iridotomy, which may reduce the risk of anterior capsular opacification and cataract formation comparing to the old forms of ICL. Previous studies have shown that the pupil constriction in response to light can affect the vault, eventually causing the ICL to move posteriorly towards the crystalline lens, leading to a significant decrease in central vault under photopic conditions.

Femtosecond (FS) laser is an infrared laser with a wavelength of 1053 nm. It works by producing photo-disruption or photoionization of the optically transparent tissue such as the cornea. Application of FS results in the generation of a rapidly expanding cloud of free electrons and ionized molecules. The acoustic shock wave generated results in disruption of the treated tissue.

FS laser has pulse duration ranging 10 to 15 seconds. Reducing the pulse duration reduces the amount of collateral tissue damage which makes FS laser safe to be used in corneal surgeries.

The Wave Scan Wave Print System (Visx, Inc.) is a diagnostic instrument designed to measure and display refractive errors and wave front aberrations of the eye using a Hartmann-Shack wave front sensor. A small spot of laser light is projected onto the retina and reflects back through the pupil. The light exiting from the eye is imaged by a lens let array, and the array of spot images is captured by a video sensor. The location of each spot gathered from the video sensor is then compared to the theoretical ideal locations, and the eye's wave front aberrations are computed. The measurements with this device are centered on the center of the entrance pupil and taken without pupil dilation.

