## SUBJECTS & METHODS

- **Type of Study:** Prospective observational study
- **Study Setting:** Magrabi Eye Hospital, Cairo, Egypt
- **Study Period:** 24 months. The patient will be assessed on interval: preoperatively, 1 month, 3 months and 6 months postoperatively.
- **Study Population:**
  - *Inclusion Criteria:*
    - Moderate myopia (-4D to -8D)
    - Age >18 years
    - Clear optical media
    - No ocular pathology
  - *Exclusion Criteria:*
    - Mild (<-4D) or high (>-8D) myopia, hyperopia
    - Patients with media opacity
    - Patients with associated ocular pathology
    - Patients with corneal topography not fitting to either treatment modalities
- **Sampling Method:** Convenience non-random sampling technique will be followed

- **Sample Size:** 120 eyes will be included in the study, and they will be divided into four groups:
  - Group 1: includes 60 eyes undergoing ICL surgery
    - Divided into two subgroups:
      - Group 1A: includes patients with simple myopia
      - Group 1B: includes patients with compound myopic astigmatism
    - Group 2: includes 60 eyes undergoing femtoLASIK surgery
      - Divided into two subgroups:
        - Group 2A: includes patients with simple myopia
        - Group 2B: includes patients with compound myopic astigmatism
- **Ethical Considerations:** This study will be conducted after the approval of the institutional ethical committee and after obtaining an informed written consent from every patient
- **Study Tools:**
  - Slit Lamp Biomicroscopy
  - Pentacam for full corneal topography profile (Oculus)
  - Wave scan J&J vision Visx for assessment of aberrations
  - PeliRobson Chart for testing of contrast sensitivity
- **Study Procedure:** Patients will be diagnosed according to:
  - Full detailed history
  - Complete clinical ophthalmological examination including visual acuity assessment with best correction, anterior segment examination, IOP measurement, fundus examination, cycloplegic refraction and contrast sensitivity testing
  - Investigations: corneal topography, aberrations screening
  - Post-operative follow up including visual acuity assessment with best correction, aberrations screening and contrast sensitivity testing on interval 1 month, 3 months and 6 months postoperatively

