**Statistical Analysis & Package:** The collected data will be revised, coded, tabulated, and introduced to a PC using statistical package for social sciences (IBM SPSS 20.0). Data will be presented and suitable analysis will be done according to the type of data obtained for each parameter.

- *Descriptive Statistics:*

- Mean, Standard deviation ( $\pm SD$ ) and range for parametric numerical data, while Median and Interquartile range (IQR) for non-parametric data

- Frequency and percentage of non-numerical data

- *Analytical Statistics:*

- Pearson Correlation Coefficient (r): Correlation was used as a measure of the strength of a linear association between two quantitative variables. The Pearson correlation coefficient, r, can take a range of values from +1 to -1. A value of 0 indicates that there is no association between the two variables. A value greater than 0 indicates a positive association; that is, as the value of one variable increases, so does the value of the other variable. A value less than 0 indicates a negative association; that is, as the value of one variable increases, the value of the other variable decreases

- P-value: Level of significance:

- P>0.05: Non significant (NS)
- P<0.05: Significant (S)
- P<0.01: Highly significant (HS)

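### Does the plan need to fix a pupil diameter, lighting and pupil adjustment for the aberration outcome?

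*Combined protocol and SAP*

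**What the plan says.** Under Study Tools in Subjects & Methods, the instrument entry is "Wave scan J&J vision Visx for assessment of aberrations". Study Procedure lists "Investigations: corneal topography, aberrations screening" at diagnosis, and after surgery "aberrations screening and contrast sensitivity testing on interval 1 month, 3 months and 6 months postoperatively". Neither entry names a metric, a Zernike order or a diameter.

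The only text on pupil state is background in the Introduction: "The measurements with this device are centered on the center of the entrance pupil and taken without pupil dilation". This describes centration and the absence of dilating drops. It does not give the diameter over which aberrations are then computed. The Introduction also indicates that higher orders are the interest: "Less high order aberrations are induced with femto LASIK compared to the conventional approach".

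The diagnostic examination includes "cycloplegic refraction and contrast sensitivity testing", and the plan does not say whether the wavefront is captured before the cycloplegic drops.

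On analysis, Statistical Analysis & Package says that "suitable analysis will be done according to the type of data obtained for each parameter". It names no pupil covariate and no between-group test. The groups are 60 ICL eyes and 60 femto LASIK eyes, and "Convenience non-random sampling technique will be followed".

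**The concern.** Higher-order aberration magnitudes depend steeply on the aperture over which they are computed. For the same optics, to leading order, third-order magnitudes grow with the cube of pupil diameter and fourth-order magnitudes with the fourth power. Undilated pupils vary with light and between people, so a natural-pupil RMS carries pupil variation as well as optical variation.

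Two harms could follow. With equal mean pupils in the two groups, the extra variation is noise and costs precision. With unequal mean pupils, the ICL versus femto LASIK comparison is biased, and non-random sampling does nothing to balance pupils. A shift between visits would bias the within-group comparison in the same way.

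Aberration is one of three listed postoperative assessments, alongside visual acuity and contrast sensitivity, so a spurious difference could reach the main conclusions. Signed coefficients whose group mean is near zero are not affected in this way.

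**Working it through.** **Inputs.** From the documents: 60 eyes per group, significance at P<0.05, one device, measurements before surgery and at 1, 3 and 6 months. The documents give no pupil or aberration data and no effect size or SD behind the 120 eyes, so there is no stated figure to reproduce. Everything else below is an assumption: reference pupil 6.0 mm, between-eye pupil SD 0.1 to 0.5 mm, optical coefficient of variation (CV) 20% to 40%.

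**1. Bias for identical optics.** The ratio of RMS values is (D1/D2)^k, with k = 3 or 4.

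| Mean pupils (mm) | k = 3 | k = 4 |
|---|---|---|
| 6.0 vs 5.9 | (6/5.9)^3 = 1.05 | (6/5.9)^4 = 1.07 |
| 6.0 vs 5.75 | (6/5.75)^3 = 1.14 | (6/5.75)^4 = 1.19 |
| 6.0 vs 5.5 | (6/5.5)^3 = 1.30 | (6/5.5)^4 = 1.42 |

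**2. Noise with equal mean pupils.** With c the CV of (d/6)^k and optical CV 30%, the variance ratio to optics alone is [(1 + c²)(1 + 0.30²) − 1]/0.30². The effective number of eyes is 60 divided by that ratio.

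| Pupil SD (mm) | c, k = 3 / 4 | Variance ratio | Effective eyes out of 60 |
|---|---|---|---|
| 0.1 | 0.050 / 0.067 | 1.03 / 1.05 | 58 / 57 |
| 0.25 | 0.125 / 0.166 | 1.19 / 1.34 | 51 / 45 |
| 0.5 | 0.248 / 0.332 | 1.75 / 2.33 | 34 / 26 |

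**3. False positives, postoperative values only.** This simulates 60 vs 60 independent eyes with identical optics, pupil SD 0.5 mm, optical CV 20% to 40% and a two-sample t-test on natural-pupil RMS. The rate of P<0.05 for third-/fourth-order RMS is:

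- equal mean pupils: 5% / 5%
- 0.1 mm difference: 8–13% / 10–15%
- 0.25 mm difference: 30–56% / 39–63%
- 0.5 mm difference: 82–99% / 92–99.5%

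**4. The same with the preoperative value used.** The plan measures the same eye before surgery. Write RMS = a·D^k, where a is the optical coefficient. Then

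log(RMS_post) − log(RMS_pre) = log(a_post/a_pre) + k·log(D_post/D_pre).

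If an eye's pupil is the same at both visits, the last term is zero. If it varies only at random around a stable mean, the term adds noise but almost no group difference.

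The simulation assumed optical CV 30%, a 1.5-fold average surgical increase in both groups that varies between eyes (CV 20–30%), and within-eye pupil SD of 0 to 0.3 mm. Over both orders:

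| Mean pupil difference | Raw change from baseline | Log change from baseline |
|---|---|---|
| 0.25 mm | 8–20% | about 5% |
| 0.5 mm | 21–62% | about 5% |

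Raw change gives partial protection. Log change restores the nominal rate, provided mean pupils are stable across visits.

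**5. Would a log-diameter covariate be a safe remedy?** It is exact only if both groups share one power law. Corneal ablation and a phakic lens need not. With equal RMS at 6 mm, exponents of 3 in one group and 4 in the other, and optical CV 30%, the covariate model rejects in about 59% of trials with mean pupils of 5.5 and 5.0 mm. With 5.5 mm in both groups it still rejects in about 36–39%.

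**The case for a change.** The strongest case for a change is that the omission is real and would be cheap to close. No section gives a diameter, lighting, metric or covariate, and the background sentence on undilated capture does not supply them. Allocation is not randomized. The scaling law is sound and the ratios in step 1 are correct. A reader of natural-pupil RMS could not tell an optical difference from a pupil difference. Computing at one diameter would need only an export setting or a rescaling, and would not alter the sample size. Baseline comparison also fails if surgery, lighting or the order of drops shifts one group's pupils between visits.

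All of that stands as a description of what is unstated. It does not show that the plan produces a wrong answer. The documents do not commit to RMS, do not say values are computed over natural pupils, and do not show that pupils differ. The high rates in step 3 come from an analysis the plan does not name, one that discards the baseline, at the largest assumed pupil difference.

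Fixing the diameter does not by itself secure a 5% error rate either, because that figure assumes independent eyes. If every patient contributed both eyes (30 patients per group) and the inter-eye correlation were 0.5 to 0.9, the fixed-diameter t-test would reject in 11–17% of trials. A fixed diameter also leaves outer wavefront data unused in larger pupils, and natural-pupil aberration is a legitimate target when the aim is visual outcomes.

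**Conclusion.** No change to the plan follows. The text is silent on metric, diameter, lighting and order of capture, but silence is all that is shown. The bias is conditional on RMS, natural-pupil computation and unequal mean pupils together. If those held, it would be about 5%/7% for a 0.1 mm difference, 14%/19% for 0.25 mm and 30%/42% for 0.5 mm (third-/fourth-order). Noise is slight at a pupil SD of 0.1 mm and substantial at 0.5 mm. These figures rest on leading-order scaling and assumed pupil values.

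An analyst can meet the point within the latitude the plan already gives, by exporting at one diameter or by comparing log change from the preoperative value, and by stating the metric, diameter and lighting with the results. If values are already exported at one diameter, only that statement is needed. Writing in a pupil-covariate model would bring its own error whenever the two procedures scale differently with diameter. This is a missing measurement detail for one of three assessments, to which the plan gives no stated priority.

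### Corrected acuity, contrast sensitivity and aberrations are all measured before surgery, but the plan specifies no ICL versus femto LASIK comparison that uses the preoperative value

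*Combined protocol and SAP*

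**What the plan says.** All places are in the combined protocol and SAP, under SUBJECTS & METHODS.

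- **Design.** The study is a "Prospective observational study". On sampling it says "Convenience non-random sampling technique will be followed". No allocation or matching rule is given.
- **Size.** "120 eyes will be included in the study, and they will be divided into four groups". The two treatment groups are "Group 1: includes 60 eyes undergoing ICL surgery" and "Group 2: includes 60 eyes undergoing femtoLASIK surgery".
- **Visits (Study Period).** "The patient will be assessed on interval: preoperatively, 1 month, 3 months and 6 months postoperatively".
- **Measurements (Study Procedure).** Before surgery: visual acuity with best correction, "fundus examination, cycloplegic refraction and contrast sensitivity testing", and, among the investigations, aberrations. The follow-up item lists corrected acuity, aberrations and contrast sensitivity again at each postoperative visit.
- **Analysis (Statistical Analysis & Package).** "suitable analysis will be done according to the type of data obtained for each parameter". Beyond that, the section names descriptive summaries, the Pearson correlation coefficient (without saying which variables) and labels for p-values. It names no test between the treatment groups, no change from baseline, no covariate and no repeated-measures model.

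**The concern.** The stated aim is to compare visual outcomes after the two procedures. Each of the three repeated measures has a preoperative value in the same eye, yet the plan does not say how that value enters the comparison.

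The type of data cannot settle this. It can decide between a t-test and a rank test. It cannot decide between postoperative values alone, change from baseline and a baseline-adjusted model, because all three apply to the same numerical data. When the groups start unequal, the three answer different questions and can disagree. As written, the choice can be made after the results are seen.

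Two things are at stake. First, groups formed without randomisation are not expected to start equal even on average, and a postoperative-only comparison passes part or all of a starting difference into the result. Second, variation between eyes that was present before surgery stays in the error term although the data to remove it are already collected.

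**Working it through.** **The plan's own figure.** The 120 eyes come with no effect size, SD or power, so the number cannot be reproduced. It is used only as 60 eyes per group.

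**Inputs.** From the documents: 60 eyes per treatment group and a significance level of 0.05 (taken as two-sided). Assumed, because the documents give neither: the pre/post correlation rho (0.3, 0.5, 0.7) and a preoperative imbalance b of 0.3 SD. Eyes are treated as independent, and pre- and postoperative SDs as equal to 1.

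**Step 1: precision.**

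- Standard error of a postoperative-only difference: sqrt(2/60) = 0.183 SD.
- Difference detectable with 80% power: (1.960 + 0.842) × 0.183 = 0.511 SD.
- Baseline adjustment multiplies the variance by 1 − rho². The equivalent number of eyes per group is 60/(1 − rho²), and the detectable difference is 0.511 × sqrt(1 − rho²).
- The variance of a change score is 2(1 − rho) times the postoperative-only variance.

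| rho | Variance ratio, adjusted | Equivalent eyes per group | Detectable difference (SD) | Variance ratio, change score |
|---|---|---|---|---|
| 0.3 | 0.91 | 66 | 0.488 | 1.4 |
| 0.5 | 0.75 | 80 | 0.443 | 1.0 |
| 0.7 | 0.51 | 118 | 0.365 | 0.6 |

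A change score is more precise than postoperative values alone only when rho exceeds 0.5. If the groups start 0.3 SD apart, the adjusted variance rises by the factor 1 + 0.3²/4 = 1.0225, giving ratios of 0.93, 0.77 and 0.52. This barely alters the picture.

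**Step 2: bias, two accounts of the same 0.3 SD imbalance.** Assume no true difference between the procedures.

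*Account A: the imbalance regresses towards the mean with correlation rho.* The bias is rho × b for postoperative-only, −(1 − rho) × b for change, and 0 for the adjusted model.

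*Account B: the imbalance is a stable group difference that would persist without surgery.* The bias is b for postoperative-only, 0 for change, and (1 − rho) × b for the adjusted model.

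| rho | A: post-only | A: change | A: adjusted | B: post-only | B: change | B: adjusted |
|---|---|---|---|---|---|---|
| 0.3 | 0.09 | −0.21 | 0 | 0.30 | 0 | 0.21 |
| 0.5 | 0.15 | −0.15 | 0 | 0.30 | 0 | 0.15 |
| 0.7 | 0.21 | −0.09 | 0 | 0.30 | 0 | 0.09 |

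**Step 3: false-positive rate of the postoperative-only test under account A.** The standardised shift is bias/0.183 = 0.49, 0.82 and 1.15. The two-sided rejection rate at the 1.96 limit is then 7.8%, 13.0% and 21.0% instead of 5%. Under account B, the adjusted model at rho 0.5 and 0.7 has bias 0.15 and 0.09 with standard error 0.158 and 0.130, a rejection rate of about 16% and 11%.

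Postoperative-only is biased under both accounts. The adjusted model and the change score are each unbiased under one of them.

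**Step 4: two eyes per patient.** The documents count eyes and do not say whether both eyes of a patient may enter. If every patient contributed two, an assumed inter-eye correlation of 0.5 gives 60/1.5 = 40 effective eyes per group, and 0.9 gives 60/1.9 = 32. At 40, the unadjusted detectable difference is 2.802 × sqrt(2/40) = 0.63 SD rather than 0.51.

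**The case against.** Five points can fairly be made on the other side.

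1. **The plan states no postoperative-only analysis.** It states no between-group test at all, so the loss is measured against a comparator that is merely permitted. This is true, and baseline adjustment is one part of a larger missing specification. The point still stands alone: naming a t-test on postoperative values would fill the larger gap and leave this problem in place.
2. **A reader might infer that the preoperative values will not be used at all.** The documents do not support that. Descriptive tables would presumably include them, the Pearson correlation names no variables, and the general analysis sentence is open-ended. What is missing is a specified group comparison that uses them.
3. **A reader might infer that change scores are wrong and should be barred, or that adjustment removes most of the bias.** Neither follows. Which method is unbiased depends on whether the baseline difference regresses or persists, and convenience sampling does not tell us. Adjustment for an outcome's own baseline also leaves confounding by refraction, age and topography. This objection stands in full and shapes the fix.
4. **The size rests on assumptions.** No correlation, SD or imbalance appears in the documents, and one range is applied to three different outcomes. Eligible eyes have clear media and no pathology, so corrected acuity may sit near a ceiling and gain little. At rho 0.3 the gain is small for any outcome. This stands as a limit on the figures.
5. **Eyes may not be independent.** If both eyes of patients enter, absolute power is lower than independence implies, and an eye-level model without a patient term could give intervals that are too narrow. This also stands.

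**Conclusion.** The concern holds in a limited form. The protocol schedules corrected acuity, contrast sensitivity and aberrations before and after surgery in non-randomised groups. The statistical section specifies no ICL versus femto LASIK comparison that uses the preoperative value. A postoperative-only comparison would satisfy the plan as written, and it is the one of the three options that is biased by a baseline difference under both accounts considered.

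The figures are illustrative. Over rho 0.3 to 0.7 the precision at stake is 9% to 49% of the variance, and under account A the excess in the false-positive rate is about 3 to 16 percentage points. They depend on the assumed correlation, the assumed 0.3 SD imbalance and independent eyes. The structural point does not depend on them: the plan should fix how baseline enters before results are seen. The documents do not support going further, to a claim that one method of handling baseline is free of bias in these groups.

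**What to change.** Add to Statistical Analysis & Package:

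- For corrected acuity, contrast sensitivity and aberrations, estimate the ICL minus femto LASIK difference at each postoperative visit from a model that includes that eye's preoperative value of the same outcome (analysis of covariance or the equivalent mixed model), and not from postoperative values alone.
- State whether both eyes of a patient can enter. If they can, include a patient effect or use cluster-robust standard errors.
- Report the group difference in change from baseline as a sensitivity analysis, and say that the two methods make different assumptions about the baseline difference. If they disagree, report both.
- State that this adjustment does not deal with confounding by refraction, age or topography.

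The cost is a few sentences of analysis wording. No visit, measurement or eye is added: the preoperative values are already scheduled, and the named package, SPSS 20, fits the model.

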## **AIM OF THE WORK**

This study aims to compare visual outcomes after Femto LASIK and implantable collamer lens in treatment of moderate myopia.

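### The sole aim is to compare femto-LASIK with ICL, but the analysis section specifies no between-group comparison, and the one inferential method it names does not estimate that difference

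*Combined protocol and SAP*

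**What the plan says.** AIM OF THE WORK contains a single objective: "This study aims to compare visual outcomes after Femto LASIK and implantable collamer lens in treatment of moderate myopia".

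SUBJECTS & METHODS describes the design as "Prospective observational study" and, on sampling, states "Convenience non-random sampling technique will be followed". It gives no rule for who receives which procedure. On numbers it says "120 eyes will be included in the study, and they will be divided into four groups": 60 ICL eyes and 60 femto-LASIK eyes, each split into simple myopia (A) and compound myopic astigmatism (B). Assessments are before surgery and at 1, 3 and 6 months. Acuity with best correction, aberrations and contrast sensitivity are followed up, and none is named as primary.

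The statistical paragraph of the same section promises analysis suited to the type of data, lists descriptive summaries, and then names one analytical method: "Pearson Correlation Coefficient (r): Correlation was used as a measure of the strength of a linear association between two quantitative variables". It does not say which two variables. The significance labels at 0.05 and 0.01 belong to no stated test.

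**The concern.** Procedure is a category, so a correlation between two quantitative variables does not address the aim. Someone who applied only the method named would finish with no estimate of how the procedures differ.

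The general promise of suitable analysis permits a comparison without fixing one. Three types of outcome at three postoperative visits give 3 x 3 = 9 outcome-visit pairs. Each could be analysed as a postoperative value, a change from baseline or a baseline-adjusted difference, by eye or by patient. These choices can give different answers from the same data, and the text lets them be made after the data are seen.

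Two features of the design make the choice matter more. Without randomisation, the groups may differ before surgery. And because the sample is counted in eyes, some patients may contribute two correlated observations.

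**Working it through.** **1. Figures to reproduce.** The 120 eyes come with no effect size, SD or power, so there is no calculation in the plan to check. The core of the point is textual: no t-test, rank test, chi-square test, ANOVA, regression, mixed model or other group contrast is named anywhere in the text.

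**2. What Pearson r can deliver.** Adding a constant to one variable leaves r unchanged. In a simulated group, r between pre- and postoperative values was 0.497 whether the outcome was shifted by 0, 0.5 or 2 SD. Pooling all 120 eyes does not help, because procedure is not one of the two variables. If procedure were coded 0/1, which the plan does not describe, the P-value would equal that of a t-test. The coefficient would still be unit-free: with equal groups r = d/sqrt(d^2 + 4), so d = 0.5 gives 0.5/sqrt(4.25) = 0.243, whether the raw difference is 0.05 (SD 0.1) or 0.5 (SD 1).

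**3. How far permitted analyses can diverge (assumed inputs).** Let the groups differ before surgery by d SD, let the pre/post correlation be r with equal SDs and a common slope, and let there be no procedure effect given baseline. The expected result is +r x d for the unadjusted comparison, -(1 - r) x d for change from baseline, and 0 for the baseline-adjusted difference. With 60 independent eyes per group, SE = sqrt(2/60) = 0.183 SD, and the unadjusted rate of false P<0.05 is Phi(-1.96 + rd/SE) + Phi(-1.96 - rd/SE).

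| d | r | Unadjusted (SD) | Change (SD) | False P<0.05, unadjusted |
|---|---|---|---|---|
| 0.25 | 0.3 | +0.075 | -0.175 | 7% |
| 0.25 | 0.5 | +0.125 | -0.125 | 11% |
| 0.25 | 0.7 | +0.175 | -0.075 | 16% |
| 0.5 | 0.3 | +0.15 | -0.35 | 13% |
| 0.5 | 0.5 | +0.25 | -0.25 | 28% |
| 0.5 | 0.7 | +0.35 | -0.15 | 48% |

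The unadjusted and change analyses differ by r x d + (1 - r) x d = d, with opposite signs. If instead the preoperative gap would persist without any procedure effect, change from baseline is unbiased and the adjusted analysis is off by (1 - r) x d.

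**4. Fellow eyes (assumed inter-eye correlation 0.5 to 0.9).** If a share s of eyes are in pairs having the same procedure, the true SE divided by the eye-level SE is sqrt(1 + s x ICC), and the false-positive rate is 2 x (1 - Phi(1.96/ratio)).
- s = 1: ratio sqrt(1.5) = 1.22 to sqrt(1.9) = 1.38; rate 11% to 16%.
- s = 0.5: ratio sqrt(1.25) = 1.12 to sqrt(1.45) = 1.20; rate 8% to 10%.
- All eyes paired, fellow eyes having different procedures: ratio sqrt(1 - ICC) = 0.71 to 0.32, so eye-level intervals are too wide.

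**5. Precision by A/B stratum (assumed 30/30 split, independent eyes).** The 95% half-width is 1.96 x sqrt(2/30) = 0.51 SD within a stratum, against 1.96 x sqrt(2/60) = 0.36 SD overall.

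**The case against.** The strongest reply is that this is an omission and not a wrong choice. The plan never assigns Pearson r to the comparison, it promises analysis suited to each parameter, and it sets up two parallel groups of 60 eyes. A comparison is plainly intended. That stands. A reader might infer that r will be used to compare the procedures, or that no comparison will be run. The documents support neither.

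A reader might also take an unadjusted eye-level comparison to be the plan's default. The text says neither unadjusted nor eye-level; that is only one of the analyses it leaves open.

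On selection, the INTRODUCTION names "Patients who are not suitable candidates for corneal reshaping procedures" among those who can benefit from ICL. This is general background and not an allocation rule, so it does not show that the ICL eyes here will be unsuitable for LASIK. SUBJECTS & METHODS limits both groups to the same range of myopia and excludes corneal topography that does not suit the treatments. The wording of that exclusion is ambiguous. If topography must suit both procedures, much of the difference in corneal suitability goes; if it need suit only one, it does not. Either way, other routes of selection remain, so imbalance is possible and not established.

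Finally, every magnitude above rests on assumed inputs, and the fellow-eye effect changes direction with a pairing pattern the plan does not state. This is correct, and the figures should not drive the severity. What survives is that the only aim has no specified analysis.

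**Conclusion.** The point holds as under-specification of the main analysis. The method named gives no ICL-minus-LASIK difference, and the general wording supplies no contrast, covariates or unit of analysis. This rests on the text alone and needs no numerical assumption. It is more than missing detail, because the groups are non-randomised and counted in eyes, so the unstated choices affect both the estimate and its standard error.

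The size for this study is unknown: the documents give no SD, pre/post correlation, preoperative imbalance, inter-eye correlation or number of patients. The tabulated shifts and error rates show what could happen under the stated assumptions. A reader might take the 48% as the expected error rate of this study; nothing in the documents supports that.

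**What to change.** In the statistical paragraph of SUBJECTS & METHODS, state as the main analysis the ICL-minus-LASIK difference with 95% CI for one outcome and one visit named in advance (6 months is one candidate). Adjust for the preoperative value of that outcome, preoperative refraction and the A/B stratum. Define the refraction term so that it does not merely repeat the astigmatism split. Account for clustering by patient with a mixed model or GEE; if all visits are modelled together, allow for repeated measurements on the same eye as well.

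Keep Pearson r as description only, and state that residual confounding remains.

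Optional secondary analyses are the 1A v 2A and 1B v 2B differences, labelled as imprecise, and a change-from-baseline sensitivity analysis. The latter should always be reported, not only when it disagrees, since it differs in expectation from the adjusted result by (1 - r) x d whenever the groups differ before surgery.

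The cost is a few sentences of wording and slightly more analysis work. Patient and eye identifiers must be kept in the data set. No new measurements are required, since preoperative refraction and contrast sensitivity, acuity and aberrations are already planned. The limitation is that only measured factors are adjusted for.
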